4.9 Method of study

For each of the **two individual studies**, a **separate** information leaflet detailing the purpose will be provided to all potential recruits (see supporting documents and flow chart- **figure 7**). If a patient is willing to participate, written consent will be obtained.

The patients will then take part in a researcher led Reproductive Health interview which includes routine demographic data and information regarding previous obstetric, medical and gynaecological history, as well as questions regarding psycho-sexual health history. Where possible, the demographic and sensitive information relating to participants such as the ethnicity, obstetric and mental health history will be obtained by the researcher from the participants notes. All information will be entered into a secure study database. Patients will be identified by study number only.

During the ultrasound examination, women will be in the supine position with flexed hips and knees and the bladder empty as previously described. Healthcare professionals will be blinded to the ultrasound findings and these findings will also not be disclosed to the parents. Another doctor or midwife will perform all the ultrasound examinations.

Fetal position will be assessed with a transabdominal scan and recorded with half hourly divisions⁷. Thereafter, the transducer will be placed transperineally at the level of the posterior fourchette in a transverse position (Figure 1), and cervical dilatation¹⁴ and head-perineum distance (HPD) measured as previously described²². Caput succedaneum will be measured in a sagittal transperineal scan^{9,15} (Figure 1). Moulding will be assessed as either present or not¹².

The healthcare professional will perform digital vaginal examination assessing cervical dilatation, fetal head descent and position. The descent will be categorised using the WHO classification of fetal head station with the ischial spines as reference point 0, -5cm at the pelvic inlet and +5cm at the pelvic outlet²⁷.

Acceptability and Feasibility:

In this group, patients will also be asked to complete two additional researcher-led questionnaires (modified from a previously validated questionnaire -see supporting documents). This will be in the form of a “pre-study” and a “post-study” questionnaire which will focus on the patient’s views regarding vaginal examinations and the transperineal scanning method to assess the acceptability of the technique.

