Transperineal ultrasound will then be carried out between gestations 24-42 weeks when a vaginal or speculum examination is otherwise also required to assess acceptability and feasibility. This scan will be done either immediately before or after the digital vaginal examination and the timing in relation the digital vaginal examination will be recorded.

Predictive Model:

In the predictive model group, there are no additional questionnaires. An admission ultrasound scan will be performed when the patient is deemed to be in established labour by the attending clinician. Subsequent scans will be performed as required at the time of routine clinical examinations typically between 2-4 hours apart.

The admission ultrasound scan will include if feasible fetal Doppler assessment of the umbilical artery, the cerebro-umbilical ratio (C/U: MCA/PI)¹⁶. Amniotic fluid index will also be measured. Fetal position will be assessed with a transabdominal scan and recorded as described above.

Dataset

Fixed variables

Maternal

Gestation

BMI, Age²⁸, Parity, Height, Ethnicity

Contraindication to vaginal examinations

Reason for avoidance of vaginal examinations

Fetal

EFW if known

Singleton

Multiple

Intrapartum

Non-USS:

Rupture of Membranes Yes/No: If Yes: Time

Spontaneous onset of labour Yes/No: If Yes: Time

Induction of Labour with prostaglandins Yes/No: If Yes: Time at insertion of prostaglandin

Syntocinon Yes/No: If Yes: Time
Epidural analgesia Yes/No: If Yes: Time

Modifiable parameters

USS Parameters: modified as labour progresses

- head position (TA ultrasound scan)
- cervical dilatation
- head-perineum distance
- caput
- moulding

Prolonged first stage of labour will be diagnosed according to national guidelines set in the UK by the National Institute of Health and Clinical Excellence (NICE) guidelines (cervical dilatation of < 2 cm in 4 hours)²⁵.

If recruited to the study, all patients will undergo normal clinical management with digital VEs or speculum examination performed as planned and in addition, ultrasound examinations before the digital VE/speculum by trained professionals. These ultrasound examinations will be blinded to the normal caregivers (midwives or doctors) so that they do not influence clinical management, though for practical reasons it will not be possible to blind the ultrasound operator to the clinical findings.

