4.14 External peer review

An earlier version of this protocol has been subject to external peer review by the British Medical Association leading to external funding (Helen Lawson Grant, awarded July 2014)

5. Study Outcome Measures

5.1 Primary measures:

1. Assessing feasibility of ultrasound by comparison with digital vaginal examinations:

- *Digital vaginal examination*: cervical dilatation, head station, caput, moulding, head position
- *Ultrasound*:
 - *Transabdominal Ultrasound*: Fetal head position
 - *Transperineal Ultrasound*: Cervical dilatation, head-perineum distance, caput and moulding

2. Acceptability of Transperineal Ultrasound to patients

3. Dataset for predictive model of outcome of labour of Caesarean section due to failure to progress and/or fetal distress

- Time to delivery

- Mode of delivery
- Primary indication for delivery
 - failure to progress
 - suspected fetal compromise

5.2 Secondary measures:

1. Neonatal outcome

- Gender
- Birth-weight
- Apgar Scores at 1 and 5 minutes
- Cord Gases
 - Fetal acidosis defined as arterial pH <7.10 and base excess >12.0mmol/l
- Neonatal unit admission within 24 hours
- Neonatal morbidity

6. Adverse events and reporting procedure

RISK ASSESSMENT - This study will not involve any risk to the participants. There are no predicted risks associated with the additional transabdominal and transperineal ultrasound scan. The scans will be used at the same settings and duration as routine ultrasound. We will be using probe covers and disinfection spray to clean the probe between patients.

The patient will be managed accordingly in concordance with local guidance and follow up arrangements will be made. The patient will still be followed up for the purposes of the study.

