7.1 Statistical and Data Analysis

In both groups, data will be collected prospectively and compared with vaginal examinations. In the second group, there will also be additional longitudinal measurements.

We will use a p value of <0.05 to indicate significance.

All measurements will be entered online at the time of examination to a secure database on the Imperial College Healthcare NHS Trust shared server where the patient will be identified by study number only. The database entry page will be accessible to investigators on their login, though they cannot interrogate data already entered. The data rules will follow closely to those performed through the recently completed multicentre European TRUFFLE study of fetal growth restriction where ultrasound measurements were captured at the time of examination³⁷.

For 24-42 weeks assessment of acceptability and feasibility:

Acceptability and preference will be tested using a questionnaire with Likert scale for discomfort, adapted from the W-DEQ Score³⁸

Feasibility of the ultrasound technique will be compared to digital VE for (a) total number of observations missing (head descent, position and cervical dilatation) during an admission on the delivery unit and (b) number of ultrasound examinations or digital VEs that could not be carried out for whatever reason where there was an intention to carry out a digital VE.

As a part of feasibility, *Reproducibility* between the *ultrasound and digital VE techniques* will be assessed both as a correlation (r) and agreement (using the Bland Altman method) between the ultrasound method and digital VE for head descent and cervical dilatation, and the Kappa statistic for head position.

Term predictive model:

The predictive value of intrapartum ultrasound parameters will be investigated using linear and logistic regression analyses. We will calculate the Receiver Operating Characteristic (ROC) curve with the Area Under the Curve (AUC) and associated positive and negative predictive values for delivery outcomes in the evaluation of transperineal ultrasound as a diagnostic tool.

8. Study supervision and Monitoring

Central and local supervision: the chief principal investigator at Imperial College London will be responsible for the protocol, quality control, interim analyses of the data, advice on progress and final analysis and reporting of the study. The Imperial Joint Research Compliance Office may audit the study as part of routine research governance.

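### Section 7.1 applies Bland-Altman to head descent, but ultrasound head-perineum distance and digital VE station are different scales with no stated conversion, so the bias is arbitrary and the limits are contaminated by scale

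*Combined protocol and SAP*

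**What the plan says.** As a part of feasibility, section 7.1 plans a correlation and "agreement (using the Bland Altman method) between the ultrasound method and digital VE for head descent and cervical dilatation", with kappa for head position.

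The two methods record descent differently:

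- **Ultrasound.** Section 4.9 has "head-perineum distance (HPD) measured as previously described". The transperineal list in section 5.1 is "Cervical dilatation, head-perineum distance, caput and moulding", and the modifiable ultrasound parameters in section 4.9 again give "head-perineum distance" as the descent item. Angle of progression appears only as earlier work in section 2.2.
- **Digital VE.** The list in section 5.1 is "cervical dilatation, head station, caput, moulding, head position". Section 4.9 states that "The descent will be categorised using the WHO classification of fetal head station", and defines "fetal head station with the ischial spines as reference point 0, -5cm at the pelvic inlet and +5cm at the pelvic outlet".

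Section 4.9 also says that ultrasound measurements are compared with the matching digital examinations. Neither that section nor section 7.1 converts HPD to station, puts both on a common scale, or defines the difference to be taken.

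**The concern.** Bland-Altman summarises the differences between two measurements of one quantity in one unit. The mean difference is read as systematic disagreement, and the limits as the range of individual disagreement. Cervical dilatation satisfies this. Head descent does not. HPD is a distance measured from the perineum, whereas station is a signed position about the ischial spines. From these definitions HPD can be inferred to fall as the head descends while station rises, although the documents do not state the direction.

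Comparison with digital VE is primary measure 1, and head descent is one of only two quantities assigned to Bland-Altman. If section 7.1 is followed as written, the team would report a bias and limits for descent that cannot be read as agreement. The alternatives would be to drop the analysis, or to choose a conversion after seeing the data.

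**Working it through.** The plan gives no limits of agreement, acceptable difference or sample size for this analysis, so there is no figure of its own to reproduce. The feasibility sample size rests on a different endpoint, parameters obtained (95% versus 82%, alpha 0.05, power 90%). The usual two-proportion formula, two-sided and without continuity correction, gives 125 per group, or 250 in total. This matches section 7 and does not depend on descent agreement.

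**Inputs.** The zero and range of the station scale come from section 4.9. The intercept a, slope b, standard deviations, correlations and error SD below are assumptions, as is HPD in cm; the documents give none of them.

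**Model.** Let S be station and HPD = a - b·S + e, with e of mean zero, independent of S, and standard deviation SDe.

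1. Raw difference, D = HPD - S:
   - bias = a - (1+b)·mean(S)
   - half-width = 1.96·√[(1+b)²·SD(S)² + SDe²]
2. HPD axis reversed, D = -HPD - S:
   - bias = -a - (1-b)·mean(S)
   - half-width = 1.96·√[(1-b)²·SD(S)² + SDe²]

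**Bias.** Take a = 4 cm, b = 0.5 and an exact relation (SDe = 0).

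| Mean station | Raw: 4 - 1.5·mean | Reversed: -4 - 0.5·mean |
|---|---|---|
| -2 cm | 7.0 cm | -3.0 cm |
| 0 cm | 4.0 cm | -4.0 cm |
| +2 cm | 1.0 cm | -5.0 cm |

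The two methods carry identical information here, yet the bias is never zero and moves with the sample. With the axis reversed and b = 1 it stops moving with mean station, but it is still -a.

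**Limits, exact relation.** With SD(S) from 1.0 to 2.0 cm and b from 0.5 to 1:

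- Raw: from 1.96 × 1.5 × 1.0 = 2.9 cm to 1.96 × 2 × 2.0 = 7.8 cm.
- Reversed: from 0 (b = 1) to 1.96 × 0.5 × 2.0 = 2.0 cm.

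**Limits, fixed SDs.** Take SD(HPD) = SD(S) = 1.5 cm. The variance of D is 4.5 - 4.5r for the raw difference and 4.5 + 4.5r for the reversed one. The last column is the 95% prediction half-width for station given HPD, 1.96 × 1.5 × √(1 - r²).

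| r | Raw | Reversed | Prediction |
|---|---|---|---|
| 0 | ±4.2 cm | ±4.2 cm | ±2.9 cm |
| -0.5 | ±5.1 cm | ±2.9 cm | ±2.5 cm |
| -1 | ±5.9 cm | 0 | 0 |

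On raw values, a stronger relation looks like worse agreement. Reversal corrects the ordering, but equal SDs are the favourable case. With SD(HPD) 0.75 cm and SD(S) 1.5 cm, the reversed limits at r = -1 are still 1.96 × (1.5 - 0.75) = ±1.5 cm, while the prediction half-width is 0.

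**Limits with real error.** Take SD(S) = 1.5 cm.

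- Raw, b = 1: ±5.88, ±5.96 and ±6.20 cm at SDe = 0, 0.5 and 1.0 cm. Real error hardly moves the limits.
- Reversed, SDe = 1.0 cm: ±2.45, ±2.05 and ±1.96 cm at b = 0.5, 0.8 and 1. The error alone gives ±1.96 cm.
- Reversed, SDe = 0.5 cm: ±1.77, ±1.14 and ±0.98 cm at the same slopes. The error alone gives ±0.98 cm.

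On the reversed axis the width therefore carries real disagreement plus a scale term, (1-b)·SD(S), which vanishes only at b = 1.

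**The case against.** The strongest counter-argument is that section 7.1 does not name HPD and does not define the difference. Raw subtraction is the least favourable reading, and a competent analyst would reverse one axis. The reversed range (0 to ±2.0 cm under an exact relation) then includes no scale effect on the width. This stands in part: the largest limits above belong to raw subtraction, to which the plan does not commit. But reversal leaves the bias at an arbitrary zero offset and leaves the scale term in the width unless b = 1, and HPD is the only ultrasound descent measure listed.

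A reader might infer that the limits say nothing about disagreement. The documents do not support this. It would follow only from an error-free relation; with error and a reversed axis, the limits can mostly reflect disagreement.

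A reader might also infer that no common scale exists anywhere. That cannot be shown. The sonopartogram figure, the supporting documents and the cited source for HPD are not available, so the point is confined to the visible text.

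Finally, no decision limit rests on descent agreement, and a correlation is planned alongside it. Both are true and limit the reach of the point. The correlation still does not supply the agreement estimate that the sentence promises.

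Repeat scans ("Subsequent scans will be performed as required at the time of routine clinical examinations typically between 2-4 hours apart") raise a separate question of which pairs enter, and the mismatch of scales does not depend on it.

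**Conclusion.** The point holds, and the plan should be changed. Applying Bland-Altman to HPD and station is wrong as written. The bias reflects arbitrary zero points under either direction of subtraction, and also mean station except when the axis is reversed and b = 1. Raw limits are dominated by the spread of station and, at fixed SDs, widen as the inverse relation strengthens. Reversed limits are inflated by scale unless b = 1.

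The mismatch follows from the plan's own definitions; only its size rests on assumed values, and the direction of HPD is inferred. The effect is confined to the head-descent agreement part of feasibility. A reader might take it to undermine primary measure 1 or the feasibility sample size as a whole. It does not: dilatation agreement, kappa for head position, the correlation, the comparison of missing or failed examinations, the sample sizes and the prediction model are unaffected.

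**What to change.** In section 7.1, restrict Bland-Altman to cervical dilatation. For head descent:

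- Keep the correlation and state that a negative sign is expected. Use a rank correlation if station is recorded in grades.
- Replace Bland-Altman with a regression of digital VE station on HPD, reporting the slope and a 95% prediction interval for station. Label this calibration, not agreement.
- Note that the interval includes digital VE error, depends on the spread of station in the sample, and is approximate if station is graded.

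Alternatively, keep Bland-Altman for descent only on HPD values converted to the station scale, with the conversion stated in section 7.1 and validated outside the analysed data.

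The cost is one or two sentences and minor programming. No new data are needed, because HPD and station are already collected.

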2.2 Study Rationale and Hypothesis

Several studies have assessed the accuracy of transabdominal ultrasound in comparison with digital VE in determining fetal head position¹⁸⁻²¹. These have concluded that digital VE fails to identify the correct fetal head position in the majority of cases, especially at cervical dilatation $\leq 3-4\text{cm}$. Although transperineal ultrasound has been used pre-labour to predict the likelihood of PPROM patients going into labour²², its feasibility has not yet been assessed in the investigation and management of women either presenting with or established in labour. Initial studies have assessed head descent¹² and rotation²³ and angle of progression in labour^{13,24} to assess the second stage of labour to predict the likelihood of spontaneous vaginal delivery, instrumental delivery or Caesarean section. However, there have not been any studies directly assessing the feasibility of transperineal ultrasound scans.

We hypothesise that transperineal ultrasound will be a feasible and acceptable technique in comparison with digital vaginal examinations for 24-42 weeks gestation.

Using the data gathered in term patients, we will develop a model to predict pregnancy outcomes. This may aid in delivery of care to pregnant women by providing a real-time online calculation tool for the likelihood of vaginal delivery and length of labour based on repeat ultrasound measurements. This will allow a more

accurate prediction of the mode of delivery and reduce the number of vaginal examinations. This will improve the information available to women and their birth partners about the progress of their labour.

We anticipate improvements to women's health with additional information allowing better decision-making during labour enhancing the accurate recording of labour to a recordable skill. Universally, it may reduce the frequency of intrusive internal examinations and associated infection and will also be potentially useful in allowing the assessment of women in whom digital VE is traumatic or contra-indicated.

Overall, it may create a paradigm shift on delivery units in an area where the standard assessments have not changed in over one hundred years allowing better provision of resources.

3. Study Objectives

Primary objectives:

1. Feasibility of transperineal ultrasound scanning
2. Acceptability of transperineal ultrasound scanning
3. Creation of a "Sonopartogram" (Figure 3); an ultrasound based labour record

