4. Prediction model of time to delivery and mode of delivery at term
 - Caesarean section due to failure to progress and/or fetal distress

Secondary objectives:

1. Creation of a digital representation of the progress of labour (Figure 4).

4. Methodology and Design

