A recent study by our group has shown that 95%¹⁵ of transperineal ultrasound parameters can be obtained compared to 82% of digital vaginal examination parameters¹⁵. With an alpha of 0.05 and a power of 90%, the minimum sample size required is 250 patients.

Labour prediction model

For the labour prediction model, there are approximately 15 variables with 10 patients needed per variable³²⁻³⁴ and an approximate 25% Caesarean section rate^{28,35,36} (the primary outcome) in the UK currently. This equates to 600 patients needed for the study.

Calculation:

$$15 \times 10 \times (100/25) = 600 \text{ patients}$$

As already discussed above, for statistical power and significance, a minimum of 42 and 250 patients is required for acceptability and feasibility respectively (24-42 weeks). For the predictive modelling, 600 patients are required (37-42 weeks).

The majority of the patients for the acceptability and feasibility samples will be recruited from the predictive modelling group (gestation 37-42 weeks). However, to allow sufficient data collection for feasibility, acceptability and development of the model, at least 700 patients will be required. As the trust has an annual delivery rate of 9000 annually, over a 24-month data collection period with a delivery rate of 18,000 across the trust, 700 patients (4%) sample size is achievable.

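### Section 7.1 offers only linear regression for time to delivery and does not say how Caesarean sections enter it; a competing-event analysis would serve the length-of-labour output better

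*Combined protocol and SAP*

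**What the plan says.** Primary objective 4 (section 3) is a "Prediction model of time to delivery and mode of delivery at term". Section 5.1 lists time to delivery under the third primary measure, described as "Dataset for predictive model of outcome of labour of Caesarean section due to failure to progress and/or fetal distress". Section 2.2 gives the intended product: "providing a real-time online calculation tool for the likelihood of vaginal delivery and length of labour based on repeat ultrasound measurements".

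The analysis of the term model in section 7.1 is one sentence on method, "The predictive value of intrapartum ultrasound parameters will be investigated using linear and logistic regression analyses", followed by ROC curves, AUC and predictive values for delivery outcomes. Section 7 (Labour prediction model) assumes "an approximate 25% Caesarean section rate" and calls Caesarean section the primary outcome.

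The plan does not pair either regression with an outcome. It does not say whether time to delivery means delivery by any mode or vaginal birth only. It does not say whether a woman delivered by Caesarean is entered at her Caesarean time, left out, or treated as censored. No time-to-event method is planned; the proportional-hazards papers in the reference list support only the events-per-variable rule.

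**The concern.** Time to delivery is the one continuous labour outcome, and logistic regression, ROC and predictive values all serve a binary one. Linear regression is therefore the only planned method that fits it. A Caesarean ends labour before it would have ended by itself. When the indication is failure to progress, this happens more often in slow labours, and these are the labours that unfavourable ultrasound findings are supposed to identify.

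Linear regression leaves two simple options. One enters the Caesarean time as though labour had run its course; the other keeps only the vaginal births. If the target is length of labour to vaginal birth, the first understates duration most where labour is slow, and the second does so whenever slow progress itself leads to Caesarean. At stake is one of the two outputs of the planned tool. Because the plan leaves the choice open, it could also be made after the data are seen, for a primary objective.

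**Working it through.** **1. The plan's own figure.** Inputs from section 7: "there are approximately 15 variables with 10 patients needed per variable", and a 25% Caesarean rate. 15 × 10 × (100/25) = 600, which reproduces the stated number. It implies 600 × 0.25 = 150 Caesareans and 450 vaginal births. There is no corresponding calculation for the time model.

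**2. Set-up.** Let x be a standardised ultrasound score, T the time to vaginal birth if labour is not interrupted, and C the time of Caesarean. The study observes the smaller of T and C, and which came first. Three least-squares slopes on x are compared: T in everyone (a benchmark that cannot be observed), the smaller of T and C in everyone (all deliveries), and T where T ≤ C (vaginal births only). The fraction kept is the fitted slope divided by the benchmark slope. The documents give no distribution of T, no strength of the ultrasound association and no split of indications, so all of these are assumptions.

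**3. One worked example.** T = 7 × exp(0.35x + 0.5e) hours, with e standard normal. C is the earlier of a decision time (mean 14 h, SD 2 h) and a constant hazard of 0.015 per hour. The decision time is a simulation device only.

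- Benchmark by formula: 0.35 × E[T] = 0.35 × 7 × exp((0.35² + 0.5²)/2) = 0.35 × 8.43 = 2.95 h per SD; 2.94 in 400,000 simulated labours.
- Caesareans: 22% overall, about 47% in women more than 1 SD unfavourable.
- All deliveries: 1.81 h per SD; 1.81/2.94 = 0.62.
- Vaginal births only: 1.54 h per SD; 1.54/2.94 = 0.52.
- Mean time above 1 SD: 13.7 h uninterrupted, 10.0 h with Caesarean times entered, 9.1 h in vaginal births only.
- Other choices for the decision time and hazard give about 1.7–2.0 h per SD (0.58–0.68) and 1.5–1.7 h per SD (0.51–0.58) respectively.

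**4. A wider grid.** There are 24 scenarios of 200,000 labours, all with a 25% Caesarean rate. T is normal (mean 10 h, SD 4 h) or log-normal (median 8 h, log-SD 0.6, fitted on the log scale). R² is 0.10, 0.25 or 0.40. The failure-to-progress share of Caesareans is 100%, 60% (two mechanisms) or 0%, with the rest unrelated to progress. Fraction of the benchmark slope kept:

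| Failure-to-progress share | All deliveries | Vaginal births only | Caesarean as censoring (Tobit/AFT) |
|---|---|---|---|
| 100% | 0.75 | 0.61–0.77 | 0.96–1.01 |
| 60% | 0.69–0.78 | 0.70–0.83 | 0.92–1.04 |
| 0% | 0.74–0.75 | 0.92–1.00 | 0.98–1.01 |

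For women in the top tenth of the score, the all-deliveries prediction is 11% too short (10.9 h against 12.2 h) to 36% too short (10.1 h against 15.8 h). In the slowest tenth of labours, 80–100% end in Caesarean when failure to progress contributes, and 39–53% when it does not.

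**5. Delivery by any mode as the target.** The smaller of T and C is then the outcome itself and is always observed, so there is no censoring bias. In the example of step 3, however, 65% of women above 1 SD have delivered by 12 h but only 44% vaginally. The remaining 65 − 44 = 21 percentage points are Caesareans, and a single predicted time does not show them.

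**6. Sample size after the change.** 450/15 = 30 vaginal births per variable for the time model; 150/15 = 10 Caesareans per variable for mode. The 600 stands.

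**The case against.** The strongest reply is that the listed outcome is time to delivery, not time to vaginal birth. Read as delivery by any mode, every time is observed and linear regression has no censoring problem. That is correct, so a reader who infers that the planned model is biased in any event goes further than the documents allow. The reply does not settle the matter, because section 2.2 promises "real-time online calculation tool for the likelihood of vaginal delivery and length of labour". An any-mode time counts a Caesarean for stalled labour as a completed labour.

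A second reply is a two-part reading: logistic regression for mode, then expected time given vaginal birth. For that conditional target, regression on vaginal births answers the question asked, and its smaller slope is not bias. Even against uninterrupted time it is nearly unbiased if Caesareans are unrelated to progress. This also stands, but the plan does not state that target, and a named indication of failure to progress makes independence unlikely.

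Other stronger readings are not supported:

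- The documents do not say that failure to progress is the main indication; they list it beside suspected fetal compromise without a split.
- Their definition of prolonged first stage is a rate of dilatation, so it does not by itself restrict such Caesareans to the longest labours.
- Women with unfavourable scans would not be given the shortest predictions. Both fitted slopes stay positive, so these women still get the longest times, only understated.
- The 38% loss of slope in the worked example (1 − 0.62) is not typical; the wider grid loses 22–31% with all deliveries.

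**Conclusion.** The point holds conditionally, as an inexpensive improvement that should be made. For a primary prediction target, the plan names no method suited to a time that a Caesarean can cut short, and does not define the target closely enough to show that none is needed. Pairing linear regression with time to delivery is an inference, though a strong one.

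If length of labour to vaginal birth is meant, about 0.6–0.8 of the ultrasound slope is kept with all deliveries pooled. With vaginal births only, about 0.5–0.8 is kept when failure-to-progress Caesareans occur, and 0.92–1.00 when Caesareans are unrelated to progress. The direction was the same in every scenario with pooled times; the sizes rest on assumed distributions and mechanisms. If delivery by any mode is meant, the shortfall is one of information and not of bias.

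The logistic model for mode, its ROC analysis and the 600 are unaffected. Caregivers are blinded to the scans, so the consequence falls on a later tool and not on the care of participants.

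**What to change.** In section 7.1, define time to delivery and replace linear regression for it with a time-to-event analysis starting at the scan from which the prediction is made. Vaginal birth is the event and Caesarean a competing event, modelled by cause-specific hazards. Report the cumulative incidence of vaginal birth and of Caesarean by fixed times, for example 4, 8 and 12 h, as the tool's length-of-labour output. Keep logistic regression, ROC and predictive values for mode of delivery.

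This does not recover the uninterrupted slope used as the benchmark above. It replaces that quantity with a better-defined one: what happens in labours where Caesareans do occur. It therefore does not need the assumption that Caesareans are unrelated to progress. The censored regression in the table does need it, if uninterrupted duration is the aim, and would call for a sensitivity analysis.

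The cost is a few sentences, slightly more analysis, and an output in probabilities over time instead of one predicted duration. Delivery time, mode and indication are already in the dataset, so neither the sample size nor data collection changes.
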